Efficacy of Laser Debridement on Pain and
Bacterial Load in Chronic Wounds
(NCT03182582)

Study Protocol

November 5, 2015

[name], Principal Investigator
Stanford University
Stanford, California 94305

PROTOCOL SYNOPSIS

Title	The assessment of bio-burden reduction and procedural pain after chronic ulcer debridement.
Sponsor	Sciton, Inc. [name] [contact]
Clinical site	Stanford Advanced Wound Care Center [name] [contact]
Rationale	Chronic ulcers are a significant source of morbidity and pain. Biofilms are present in all chronic ulcer types. Additional methods for safe, effective, and tolerable chronic ulcer bed debridement are needed.
Study design	Randomized-controlled cross over, open label study
Primary objective	To determine the efficacy of the reduction of bioburden in chronic ulcers after laser and sharp debridement.
Secondary objectives	To determine the tolerability of laser and sharp debridement of chronic ulcers.
Number of subjects	Twenty
Subject selection inclusion criteria	
 • Aged eighteen years or older • Having a non-healing chronic ulcer of any etiology present for at least four weeks • Willing and able to adhere to protocol requirements • Signed Informed Consent Form prior to any study related procedure
Subject selection exclusion criteria	
 • Any unstable medical condition • Documented medical history of any significant disease or condition • Documented medical history of immunosuppression • Receiving dialysis • Having osteomyelitis • Pregnancy • Participation in another clinical study involving ulcers within thirty days prior to enrollment
Control treatment	Sharp (scalpel or curette) debridement with standard of care
Test treatment	Laser debridement with standard of care
Duration of subject participation	Subjects will be enrolled in the study for two weeks
Duration of study	The total duration of the study is expected to be six weeks. Recruitment and enrollment: up to four weeks Treatment: two weeks
Prohibited concomitant medications	Current topical or systemic antibiotic therapy
Efficacy evaluations	Significant bioburden reduction as determined by quantitative polymerase chain reaction (PCR) analysis after the debridement procedures.

Primary endpoint	Comparison of the two treatment modalities to reduce bioburden as determined by quantitative polymerase chain reaction (PCR) analysis, DNA sequencing.
Secondary endpoint	Comparison of the procedural pain from the two treatment modalities as determined by subject reported visual analog scale (VAS) pain scores. Comparison of the procedural bleeding from the two treatment modalities as determined by physician assessment. Procedural bleeding
Other evaluations	Overall subject satisfaction from the two treatment modalities.
Safety evaluations	Incidence of adverse events.
Planned interim analysis	Serious adverse events will be audited by the study team on an ongoing basis throughout the study duration.
Primary statistical analysis plan	Treatment effectiveness will be assessed by a two-sample t-test comparing the evaluation criterion at the two study intervals.
Rationale for number of subjects	This is a pilot study to determine treatment feasibility and efficacy.

SUBJECT INCLUSION CRITERIA

A subject will be eligible for inclusion in this study if ALL of the following criteria apply:

[figure not shown]
- Aged eighteen years or older
- Having an ulcer of any etiology
- Has signed the informed consent form prior to any study protocol related procedure
- Willing and able to adhere to protocol requirements

SUBJECT EXCLUSION CRITERIA

The subject will not be eligible for study inclusion if ANY of the following criteria apply:

- Any unstable medical condition that would cause the study treatment to be detrimental to the subject, as judged by the Principle Investigator
- Documented medical history of significant cardiac, pulmonary, gastrointestinal, endocrine (*other than Diabetes Mellitus type 1 or 2*), metabolic, neurological, hepatic or nephrologic disease would impede the subject's participation, as judged by the Principle Investigator
- Documented medical history of immunosuppression, immune deficiency disorder, or currently using immunosuppressive medications
- Having clinical presentation of active osteomyelitis
- Pregnancy or lactation
- Participation in another clinical study involving ulcers within thirty days prior to enrollment

STUDY DESIGN

ULCER DEBRIDEMENT

Multiple methods can be used for ulcer debridement, however evidence supporting a superior method is still lacking. Sharp debridement uses scalpel, scissors, curette, or other instruments to remove the necrotic tissue. Sharp debridement is the current standard of care, and produces rapid results. The major drawbacks of sharp debridement include the lack of a uniform technique and the potential for bacterial cross contamination. Sharp debridement may also result in bleeding or damage to underlying tissue structures.

The method of laser debridement is based upon the well-established efficacy of laser skin resurfacing utilized in dermatology and plastic surgery. The laser energy will provide controlled vaporization of the superficial layers of the ulcer bed. The potential advantages of laser debridement include precision and uniformity of tissue ablation, reduced trauma to the ulcer bed, improved patient comfort, enhanced biofilm clearance, and promotion of ulcer healing. Anecdotally, laser debridement has shown a decrease in procedural pain scores, thereby facilitating a more complete debridement.

Ulcers will be treated with a fully ablative erbium-doped yttrium aluminum garnet (erbium) laser treatment. The erbium laser system (Sciton, Inc.) has the FDA clearance for use in surgical applications requiring the excision, incision, ablation, vaporization, and coagulation of soft tissue.

The laser system is comprised of five interconnected components:

1. Laser Console - The laser console is connected to the footswitch, the articulated arm, and the user screen. The laser console houses the laser and the power supply.
2. Footswitch - The footswitch is connected to the laser console. Footswitch depression by the clinician enables laser energy delivery.
3. Articulated Arm - The articulated arm is connected to the laser console and the handpiece. The articulated arm rotates and is used to deliver the laser energy.
4. Handpiece - The handpiece is connected to the articulated arm, and steers the pattern of energy onto the patient.
5. User Screen - The user screen is connected to the console, and serves as an interface to allow the clinician to select different laser applications or laser treatment parameters.

The laser provides precise control over the depth of ablation per pass, ranging from twenty five to two hundred microns. Ablation depth is tunable in twenty five-micron increments. The laser system handpiece allows the laser beam to be scanned to form two-dimensional spots onto the pattern size. The range of the pattern size is 0.64 - 9.00 centimeters squared. The handpiece scanner provides complete and uniform application of the laser energy. This application will cover forty percent of the surface within the scanned pattern. An aiming beam, displayed as a red square on the intended treatment surface, allows the clinician to visualize the treatment area. The laser energy will be delivered inside this red square. The adjoining scans will be delivered without gaps or overlaps to ensure even treatment.

Protective eye shields to safeguard against laser light exposures will be provided to the subjects and personnel in treatment room. The eye shields will remain in place until after the completion of the laser treatment. The thermal destruction of tissue creates a smoke by-product. A smoke evacuator attached to the laser handpiece will immediately remove any smoke generated throughout the laser treatment. This removal will prevent the smoke and debris from irritating the ulcer bed.

Laser ablation will be continued until the slough tissue is completely removed. Patient pain and pinpoint bleeding will represent the clinical endpoint of laser debridement. Pinpoint bleeding signifies the laser energy approaching the healthy underlying tissue. Laser debridement will be administered to only slough tissue and ulcer edges. Healthy granulation tissue in the ulcer bed will not be laser treated. After the completion of the laser debridement procedure, sterile gauze will be used to gently clean the ulcer bed to remove any remaining debris.

STUDY SCHEDULE

Screening and Enrollment (Study Week One):

- Obtain signed Informed Consent Form
- Review medical history to determine eligibility
- Perform medical examinations needed to determine eligibility

- Collect ulcer measurements and photos
- Randomize patients to treatment groups
- Provide subjects instructions needed for study participation
- Immediately proceed to the Treatment

Treatment (Study Week One):

1. Before debridement procedure:
 - Record VAS pain score, Present Pain Intensity, and Brief Pain Inventory
 - Collect ulcer photos and measurements
 - Collect biopsies
2. Apply anesthetic
3. Perform debridement procedure
 - Record technique or laser settings used during treatment
4. After debridement procedure:
 - Collect ulcer photos
 - Record VAS pain score, Present Pain Intensity, and Brief Pain Inventory
 - Record bleeding assessment
 - Collect biopsies
 - Provide Standard of Care

Follow Up Visit (Study Week Two):

- Subjects cross over to other study group
 - Remove ulcer dressing
1. Before debridement procedure:
 - Record VAS pain score, Present Pain Intensity, and Brief Pain Inventory
 - Collect ulcer photos and measurements
 - Collect biopsies
 2. Apply anesthetic
 3. Perform debridement procedure
 - Record technique or laser settings used during treatment
 4. After debridement procedure:
 - Collect ulcer photos
 - Record VAS pain score, Present Pain Intensity, and Brief Pain Inventory
 - Record bleeding assessment
 - Collect biopsies
 - Provide Standard of Care

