Efficacy of Laser Debridement on Pain and Bacterial Load in Chronic Wounds (NCT03182582)

Statistical Analysis Plan

February 6, 2018

[name], Principal Investigator
Stanford University
Stanford, California 94305

Methods:

This is a prospective, randomized, controlled, crossover clinical trial, entailing two groups: 1) one group receiving a single laser debridement session first, followed by a single sharp debridement session one week later; 2) the other group receiving a single sharp debridement session first, followed by a single laser debridement session one week later. Analysis variables include pain during debridement, pre- and post-debridement wound sizes, pre- and post-debridement bacterial loads, and patient preference.

Statistical Analysis:

The a priori power analysis presumes a 50% reduction in patient-reported pain. A sample size of 22 patients would be required to achieve 80% power, using a two-tailed test with $\alpha = 0.05$. Descriptive analyses include means (standard deviation). A paired t-test was planned to evaluate continuous data, and the 3x2 Fisher's exact test was planned to analyze categorical data. For all data analyses performed in the study, $p < 0.05$ is considered statistically significant.

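### The protocol's efficacy criterion has no comparator and does not match its comparative primary endpoint, and neither document's t-test names the laser-versus-sharp contrast

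*Protocol*

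**What the plan says.** The Protocol Synopsis speaks to bioburden in four rows.

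- Primary objective: "To determine the efficacy of the reduction of bioburden in chronic ulcers after laser and sharp debridement". Both methods are named, but no contrast between them and no test.
- Efficacy evaluations: "Significant bioburden reduction as determined by quantitative polymerase chain reaction (PCR) analysis after the debridement procedures". There is no comparator, and the word significant is not defined.
- Primary endpoint: "Comparison of the two treatment modalities to reduce bioburden as determined by quantitative polymerase chain reaction (PCR) analysis, DNA sequencing". This is a laser-versus-sharp comparison. The pain and bleeding endpoints in the next row are comparisons too.
- Primary statistical analysis plan: "Treatment effectiveness will be assessed by a two-sample t-test comparing the evaluation criterion at the two study intervals". Neither the criterion nor the intervals are defined.

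The SAP is dated later. Its Methods section describes the design: "This is a prospective, randomized, controlled, crossover clinical trial, entailing two groups", with each patient receiving both procedures one week apart in one order or the other. On the data it says: "Analysis variables include pain during debridement, pre- and post-debridement wound sizes, pre- and post-debridement bacterial loads, and patient preference". On the tests it says: "A paired t-test was planned to evaluate continuous data, and the 3x2 Fisher's exact test was planned to analyze categorical data". The pair in the paired t-test is not identified, and no change score or between-method difference is defined.

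**The concern.** The efficacy row and the primary endpoint put different questions, and a trial can answer yes to one and no to the other. Whether the load falls after a procedure is a before-after question within one method. Whether laser lowers it more than sharp is the comparison that randomisation and crossover were set up to answer. Since both procedures remove or vaporise surface tissue, some fall is expected after either, and a before-after test alone cannot show that laser adds anything.

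The analysis sentences should settle which question governs, and they do not. An analyst could therefore follow the text faithfully and never test the primary endpoint. The stake is a conclusion about laser against sharp that rests on two uncontrolled before-after series, or on a contrast between weeks.

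**Working it through.** **1. The plan's own figure.** The SAP's 22 patients (80% power, two-tailed alpha 0.05) are based on a 50% reduction in pain. No SD, baseline mean or correlation is given, so the number cannot be reproduced. Solved backwards for a paired t-test, it implies a standardised effect of 0.626 (normal approximation: (1.960 + 0.842)/√22 = 0.597). This concerns pain and gives no information on power for bioburden. The protocol's 20 subjects carry no power calculation.

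**2. What the analysis sentences permit.** Each patient has biopsies before and after each debridement, so there are four loads per patient: laser pre and post, sharp pre and post. Three tests fit the wording.

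| Test | Fits the protocol's analysis row? | Fits the SAP's paired t-test? | Tests the primary endpoint? |
|---|---|---|---|
| Pre versus post, within each method | Yes, if the intervals are before and after | Yes; pre and post loads are the listed variables | No |
| Week one versus week two | Yes, if the intervals are the study weeks | Yes | No |
| Laser change minus sharp change, within patient | Only if the intervals are taken to mean the methods | Yes | Yes |

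**3. Why a week-one-versus-week-two test misses the endpoint.** Let L and S be the mean changes under laser and sharp, π1 and π2 the period effects, n1 the number receiving laser first and n2 the number receiving sharp first. The expected week-one minus week-two difference is

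(n1 − n2)/(n1 + n2) × (L − S) + (π1 − π2).

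With equal sequence groups (10 and 10, or 11 and 11) the first term is zero whatever the value of L − S, and only the period difference is left. The sequence ratio is not stated.

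**4. What separate before-after verdicts would do.** Suppose both methods have the same true reduction and each is judged by its own two-sided p < 0.05. With within-method power p and independent results, the chance that exactly one is significant is 2p(1 − p):

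- p = 0.50: 2 × 0.50 × 0.50 = 50%
- p = 0.80: 2 × 0.80 × 0.20 = 32%
- p = 0.90: 2 × 0.90 × 0.10 = 18%
- p = 0.95: 2 × 0.95 × 0.05 = 9.5%, about 10%
- p = 0.99: 2 × 0.99 × 0.01 = 2%

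Positive correlation between a patient's two reductions lowers these figures. Simulation with n = 20 and 50,000 runs per cell gave:

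| Within-method power | Correlation 0 | 0.3 | 0.5 | 0.7 |
|---|---|---|---|---|
| 50% | 49.8% | 41.6% | 34.6% | 26.4% |
| 80% | 31.7% | 27.3% | 22.9% | 18.0% |
| 90% | 17.8% | 15.8% | 13.8% | 11.0% |

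With n = 22 the results agree within about 1 percentage point. A direct paired t-test of laser change minus sharp change rejected in 4.8% to 5.2% of runs throughout.

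**The case against.** A reader might infer that the protocol defines success as separate significance within each method, to the exclusion of a laser-versus-sharp difference, and so plans to declare one method effective and the other not. The documents do not support that. The primary, pain and bleeding endpoints are all comparisons, and the synopsis names a control and a test treatment. The primary objective does not ask for significance and does not ask about each method separately. The Efficacy evaluations row sits alongside rows for other and safety evaluations and is not labelled a decision rule. No sentence plans to lay two within-method p-values side by side. The SAP does not repeat the efficacy row at all.

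The size is also open to challenge. If debridement of either kind nearly always lowers the load, within-method power is high. At 99% the split rate of 2% is below the 5% error of the direct test. That is correct, and it is why no single figure should be quoted. It does not rescue separate tests, though: if sharp has 99% power, the chance that laser alone is significant is at most 1 − 0.99 = 1%, however much better laser is. The approach then cannot show a laser advantage.

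Finally, this is a pilot, and whether each method lowers the load is a fair pilot question. That stands: forbidding within-method p-values would be a matter of preference. What also stands is that neither document names the primary contrast.

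**Conclusion.** The concern holds as a mismatch and an omission. The efficacy criterion lacks the comparator that the primary endpoint requires, and neither the protocol's two-sample t-test nor the SAP's paired t-test says that laser is compared with sharp. Before-after tests within each method, or a week-one-versus-week-two test, would comply with the wording and leave the primary endpoint untested. Changing the two-sample test to a paired one does not cure this, because the pair remains unnamed.

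If separate before-after verdicts were used, equal methods would be split in anything from 50% of trials (within-method power 50%) to 2% (power 99%) under independence, and less often with positive correlation, against 5% for the direct paired test. The range assumes equal true reductions and two-sided 0.05 tests. Power and correlation are assumptions throughout, since the documents give no effect, SD or correlation for bioburden. The case for a change rests on the text; the figures show only what the ambiguity could cost.

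**What to change.** Reword three places so that they state one contrast.

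- Synopsis, Efficacy evaluations: efficacy is judged by the within-patient difference, laser minus sharp, in pre-to-post change in bioburden by quantitative PCR.
- Synopsis, Primary statistical analysis plan: drop the reference to study intervals and test that same difference, reported with its estimate and confidence interval.
- SAP, Statistical Analysis: name the pair in the paired t-test as each patient's change under laser and change under sharp, for bacterial load.

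The primary objective can be reworded to match. Before-after changes within each method may stay as secondary or descriptive results, with a sentence saying that significance in one method and not in the other is not evidence of a difference.

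The cost is wording only: the scheduled biopsies already supply the four loads, so no visit, sample or procedure changes. The downside for the sponsor is that a significant reduction after laser would no longer count as the primary efficacy claim.

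### The protocol's primary test, a two-sample t-test at two undefined study intervals, does not suit the crossover, and no text says that the SAP's paired t-test replaces it

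*Protocol*

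**What the plan says.** The Protocol Synopsis gives the design as "Randomized-controlled cross over, open label study". The Study Schedule has "Randomize patients to treatment groups" in Study Week One and "Subjects cross over to other study group" in Study Week Two. The SAP (Methods) spells out the sequences: "one group receiving a single laser debridement session first, followed by a single sharp debridement session one week later", with the reverse order in the other group.

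The primary endpoint row of the synopsis is a contrast between treatments: "Comparison of the two treatment modalities to reduce bioburden". The efficacy evaluations row is worded as a change within a session: "Significant bioburden reduction as determined by quantitative polymerase chain reaction (PCR) analysis after the debridement procedures". The schedule supports both, since "Collect biopsies" appears before and after debridement in each week.

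The row headed primary statistical analysis plan says "Treatment effectiveness will be assessed by a two-sample t-test comparing the evaluation criterion at the two study intervals". Neither the criterion nor the intervals are defined, and neither term is used again.

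The SAP, dated February 2018 against November 2015 for the protocol, plans a paired t-test for continuous data and lists bacterial loads before and after debridement among its variables. It does not mention the protocol's two-sample test, and it does not say which two values form a pair.

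**The concern.** The endpoint asks whether laser or sharp debridement reduces bioburden more. In this design each patient supplies both answers, so the natural analysis is a within-patient laser-sharp difference. The protocol sentence does not describe that. Its most literal readings test a different contrast or discard the pairing. The SAP names a more suitable test, but it leaves two things to inference: that it overrides the protocol, and that its pairs are laser with sharp and not before with after. A pre-post pairing stays open because the SAP lists pre- and post-debridement values. At stake is whether the test reported as primary answers the primary question, and whether a reader can confirm that it was fixed in advance.

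**Working it through.** **Inputs.** From the documents: 20 patients (Protocol Synopsis), two-sided α = 0.05 (SAP), two sequences one week apart. Assumed: outcome SD 1; within-patient correlation ρ = 0, 0.3, 0.5 or 0.7; no carryover; no period effect in the simulations. The documents give no SD, correlation or expected bioburden effect.

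**The plan's own figure.** The SAP's 22 patients for 80% power cannot be reproduced, because it rests on a 50% reduction in pain with no SD or correlation. If the test is taken as paired, 22 patients and 80% power imply a standardised within-patient effect d_z of about 0.626. At the protocol's 20 patients that gives about 76% power. I use 76% only as a common anchor; it is not an estimate for bioburden. Exactly 76% needs d_z ≈ 0.628.

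**Reading A, week one against week two.** Let τ be laser minus sharp and π the week-two-minus-week-one period effect. A sharp-first patient has expected week-two-minus-week-one difference π + τ; a laser-first patient has π − τ. Averaged over N patients:

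E[difference] = π + τ(n_sharp-first − n_laser-first)/N.

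- At 10:10: π + τ(0)/20 = π. The treatment effect is gone.
- At 12:8 either way: τ is multiplied by ±4/20 = ±0.2.

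**Reading B, before against after debridement.** This asks whether bioburden falls during a session. It fits the efficacy evaluations row, but a fall under both treatments says nothing about which is better. No power figure applies.

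**Reading C, laser against sharp as independent samples.** The contrast is right. The test assumes a variance for the mean difference of 2/N, while the true variance is 2(1 − ρ)/N. The standard error is therefore too large by a factor 1/√(1 − ρ): 1.20 at ρ = 0.3, 1.41 at 0.5, 1.83 at 0.7, and 1 at zero.

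**Illustration.** Effect τ = d_z√(2(1 − ρ)), sequences 10:10, 40,000 simulated trials per setting:

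| ρ (assumed) | τ in SD | Paired power | C: power | C: type I error | A: rejects |
|---|---|---|---|---|---|
| 0 | 0.89 | 76% | 78% | 5% | 3% |
| 0.3 | 0.74 | 76% | 65% | 2.1% | 1.3% |
| 0.5 | 0.63 | 76% | 48–49% | 0.8% | 0.5% |
| 0.7 | 0.49 | 76% | 23% | 0.1% | 0.1% |

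**Which ρ applies.** The relevant ρ is the correlation between a patient's two pre-to-post changes, not between raw loads. If load is a stable patient level plus independent visit variation, and patients respond alike, the level drops out of each change and ρ is zero even when raw loads correlate strongly. A positive ρ requires that some patients respond more than others to both treatments. The top row is therefore a realistic case.

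**The case against.** The strongest reply is that the SAP already settles the matter. It is later, it is the dedicated analysis document, it describes the two sequences, and it plans a paired test. Taken with the primary endpoint row, laser-sharp pairing is the most coherent reading. This largely stands: the SAP most naturally supersedes the synopsis line. What remains is that no text says so, and that the pair is unnamed.

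Second, a two-sample t-test can be valid in a crossover. Comparing the sequence groups on within-patient period differences is standard and nearly as powerful as the paired test. Comparing the groups in week one only is valid too, though weak (about 35%, 26% and 18% power at ρ = 0.3, 0.5 and 0.7). That is correct, but the sentence mentions neither sequence groups nor within-patient differences. Equally, its opening words are about treatment effectiveness, so a pure week-against-week test is unlikely to be what the authors meant. The fault lies in the wording and does not show intent.

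Third, a reader might infer inflated type I error, by supposing that the groups are tested in both weeks and either result counts. No text proposes two tests. At 10:10, readings A and C do not exceed 5% when there is no treatment or period effect; with positive ρ they fall below it.

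**Conclusion.** The point holds in a limited form. The protocol's stated primary test does not suit the design, it conflicts with the SAP's paired test, and neither document reconciles the two or names the pair. The cancellation at equal sequences is algebra and needs no assumption about variance or correlation. The power figures are conditional: they rest on assumed correlations and a borrowed 76% anchor, and with uncorrelated change scores the independent-samples test loses nothing.

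Two stronger conclusions are tempting and unsupported. One is that the trial can be expected to lose power on the scale of the lower rows of the table; the documents give no correlation, and the probable governing test is the paired one. The other is that the test was chosen after the data were seen; the gap leaves room for that, but nothing in the documents shows it. Nor is the SAP's paired t-test in error for lacking a period term. In a 20-patient study described as a pilot, with a later SAP that points the right way, this should be fixed but does not invalidate the plan.

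**What to change.** Replace the synopsis sentence, and put the same statement in the SAP:

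> The primary analysis is a paired t-test of laser minus sharp, within patient, on the pre-to-post change in bacterial load; this replaces the two-sample t-test in the protocol.

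Date the change, and say so if data have already been analysed. The cost is one sentence in each document, with no extra patients, data or loss of power.

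Optionally, and as an improvement only, add a supporting period-adjusted result: within-patient period differences compared between the two sequences. It uses one degree of freedom (18 instead of 19). From the noncentral t with d_z = 0.628 and noncentrality 2d_z/√(1/n₁ + 1/n₂), power is about 75.7% at 10:10 (2 × 0.628/√0.2 = 2.81) and about 74% at 12:8, against 76% for the paired test.

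### The primary bioburden endpoint rests on biopsies whose sites are neither paired nor tied to debrided tissue, and week-one randomization precedes the baseline biopsies and pain scores in an open-label trial

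*Protocol*

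**What the plan says.** - **Endpoint.** The Protocol Synopsis defines the primary endpoint as "Comparison of the two treatment modalities to reduce bioburden as determined by quantitative polymerase chain reaction (PCR) analysis, DNA sequencing". The SAP (Methods) lists bacterial loads before and after debridement among the analysis variables and adds no sampling rule.
- **Tissue treated.** Study Design, Ulcer Debridement, states "Laser debridement will be administered to only slough tissue and ulcer edges" and then "Healthy granulation tissue in the ulcer bed will not be laser treated". The same section describes sharp debridement as a way of removing necrotic tissue and concedes that its technique is not uniform.
- **Sampling.** In the Study Schedule the instruction, before and after each procedure in both weeks, is "Collect biopsies". Site, number, size, depth, tissue type and pairing are not stated. Nor is the person who takes the sample.
- **Order.** "Randomize patients to treatment groups" stands under Screening and Enrollment. The baseline pain scores and pre-debridement biopsies come in the Treatment block that follows. The Synopsis calls the trial a "Randomized-controlled cross over, open label study".
- **Coverage.** Study Design says both "The handpiece scanner provides complete and uniform application of the laser energy" and "This application will cover forty percent of the surface within the scanned pattern". It also says that adjoining scans leave neither gaps nor overlap, and calls the treatment fully ablative.

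**The concern.** A change in bacterial load measures debridement only if both biopsies sample comparable tissue and the second comes from tissue that was debrided. The schedule secures neither. One patient could have slough sampled before and spared granulation tissue after; another could have the same slough zone sampled twice. Both would follow the Protocol, and the two results would measure different things.

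The crossover does not remove the problem, because sites are chosen afresh each week. In week one they are chosen after randomization; in week two the treatment follows from the crossover. Neither document describes a blinded sampler. The week-one baseline pain scores are exposed in the same way, and pain is the Protocol's secondary endpoint and the basis of the SAP's power statement.

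At stake is whether the laser-sharp difference reflects the procedures or the choice of sites. If locations are not recorded, no later analysis can separate the two.

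**Working it through.** **No plan figure to reproduce.** The SAP's 22 patients rest on a 50% reduction in pain. Neither document gives a bioburden effect, a variance or the share of the ulcer that is spared. Every value below other than the 20 subjects in the Synopsis is therefore an assumption.

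**Step 1: what one pair measures.** Let slough carry a load of L log10 before treatment and spared granulation tissue L − d. Debridement lowers treated tissue by R; spared tissue is assumed unchanged. The measured reduction is the pre value minus the post value. Take R = 1.

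| Pre site | Post site | Reduction | d = −0.5 | d = 0 | d = 0.5 |
|---|---|---|---|---|---|
| Slough | Treated slough | R | 1.0 | 1.0 | 1.0 |
| Granulation | Spared granulation | 0 | 0 | 0 | 0 |
| Slough | Spared granulation | d | −0.5 | 0 | 0.5 |
| Granulation | Treated slough | R − d | 1.5 | 1.0 | 0.5 |

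Only the first row measures debridement whatever d is. The mixed rows can overstate or understate it.

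**Step 2: mean difference between arms.** Suppose pre and post sites match in tissue type, but a fraction g of pairs comes from untreated tissue. An arm's mean reduction is R(1 − g), so laser minus sharp is R(g_sharp − g_laser) when both have the same true effect. With R = 1:

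- g_laser = 0.25, g_sharp = 0: 0 − 0.25 = −0.25 log10
- g_laser = 0.25, g_sharp = 0.25: 0
- g_laser = 0, g_sharp = 0.25: +0.25 log10

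The sign depends on two fractions that the documents do not give.

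**Step 3: noise when the arms are equal.** Location alone gives one pair a variance of R²g(1 − g). With independent site choice in the two weeks, the within-patient laser-sharp difference has SD = R√[2g(1 − g)], and its mean over 20 patients has SE = SD/√20. With R = 1:

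| g in both arms | SD of difference | SE, n = 20 |
|---|---|---|
| 0.10 | √0.18 = 0.42 | 0.09 |
| 0.25 | √0.375 = 0.61 | 0.14 |
| 0.50 | √0.50 = 0.71 | 0.16 |

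This is in addition to biological and assay variation, and it is there even when the mean bias is zero.

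**Step 4: order of events.** Week one as listed runs: ulcer photographs, randomization, baseline pain scores, further photographs, pre-debridement biopsies, anesthetic, debridement. Everything after the second item can be done with the allocation known.

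**The case against.** **Sharp may be selective too.** A reader might infer a bias against laser, since only laser has an explicit sparing rule. The documents do not support that: the Protocol describes sharp debridement as aimed at necrotic tissue, and with equal sparing step 2 gives zero. This stands. It leaves the noise and the mixed pairs, which affect both arms.

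**Sparing may be a real property of the treatment.** The primary objective concerns bioburden in chronic ulcers, not in debrided slough. If a treatment leaves part of the ulcer alone, a smaller whole-ulcer reduction is a result and not an error. This also stands, but a whole-ulcer endpoint would need a sampling rule of its own, and free choice of site serves neither target.

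**The sampler is not named.** A reader might infer that the person who debrides also picks the sites, and picks the second after seeing the result. Neither document says who samples or when the site is chosen, and bacterial load cannot be seen at the bedside. The supported statement is narrower: nothing prevents a choice made with the treatment known.

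**The forty percent figure.** A reader might conclude that laser could lower the load by at most −log10(0.6) = 0.22 log10. That assumes a single pass, or passes landing on the same spots, while the Protocol continues ablation until all slough is gone. The figure conflicts with its neighbors, but it does not bound the treatment effect.

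**Spared tissue may be absent or may change.** An ulcer without healthy granulation tissue has none to spare for that reason, and gauze cleaning of the bed after laser could lower the load in spared tissue. So g and zero change remain assumptions.

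**It is a one-center pilot.** This limits differences in practice between centers. It does not fix the sampling site from patient to patient or week to week.

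**Conclusion.** The point holds as a gap in sampling and in the order of events, in both arms. The specimens for the primary endpoint are not paired by site or tied to debrided tissue, and week-one baseline biopsies and pain scores follow randomization in an open-label trial. The consequences are location noise and possible selection bias.

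Direction and size cannot be derived. The illustration gives an SD of 0.42 to 0.71 log10 in the within-patient difference from location alone. It rests on a 1 log10 effect, 10% to 50% of pairs from untreated tissue in each arm, no change in that tissue, and independent site choice in the two weeks. It shows that the noise could be material beside a 1 log10 effect; it does not predict it. No revised sample size follows.

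The statements on scan coverage are a separate inconsistency, and the sampling point does not depend on them.

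**What to change.** 1. **Order in week one.** In the Study Schedule, move the randomization step to after the baseline pain scores, photographs, site marking and pre-debridement biopsies.
2. **Paired sites, both arms and both weeks.** Take the existing pre and post biopsies from adjacent sites that, before debridement, are of the same tissue type and lie within the area to be debrided (slough or ulcer edge). Use the same number and size in both arms. Allowing the edge covers ulcers without slough and slough already removed in week one.
3. **Marking.** Mark both sites on the pre-debridement photograph before debridement starts. In week two the treatment is already known, so marking only prevents a later choice of the post-debridement site; it does not hide the treatment when the sites are picked.
4. **Separately,** reconcile the forty percent statement with the statements of complete and uniform application, of scans without gaps, and of fully ablative treatment. The documents do not show which is meant.

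**Cost.** Protocol wording and a mark on a photograph already scheduled. Sampling occasions do not change, although the number of biopsies, now unstated, must be written down. The allocation has to be opened during the visit, after the baseline biopsies. The main downside is that the endpoint then describes the debrided area and not the whole ulcer, and the report must say so.
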